#### LIST OF ABBREVIATIONS

This is not an exhaustive list.

Any additional abbreviations used within the protocol must also be added here.

AE	Adverse Event
AR	Adverse Reaction
CI	Chief Investigator
ECRF	Case Report Form
CSR	Clinical Study Report
СТА	Clinical Trial Authorisation
CTIMP	Clinical Trial of Investigational Medicinal Product
iDSMC	Independent Data Safety and Monitoring Committee
DSUR	Development Safety Update Report
eECRF	Electronic Case Report Form
ECTU	Edinburgh Clinical Trials Unit
EDD	Estimated Date of Delivery
GCP	Good Clinical Practice
GDM	Gestational diabetes mellitus
GMP	Good Manufacturing Practice
HDPE	High Density Polyethylene
HIV	Human Immunodeficiency Virus
IB	Investigator Brochure
ICH	International Conference on Harmonisation
IMP	Investigational Medicinal Product
ISF	Investigator Site File
ISRCTN	International Standard Randomised Controlled Trials Number
LMIC	Low and middle income countries
NICE	National Institute for Health and Care Excellence
pECRF	Paper Case Report Form
PI	Principal Investigator
PIL (PIS)	Patient Information Leaflet (Sheet)

PAPAGENO: Protocol Version 1.0 07/03/2019 Page 9 of 46

PMG	Project Management Group	
PMPB	Pharmacy Medicines and Poisons Board (Malawi)	
QA	Quality Assurance	
QMRI	Queen's Medical Research Institute (Edinburgh)	
QP	Qualified Person	
RCOG	Royal College of Obstetricians and Gynaecologists	
REC	Research Ethics Committee	
ROM	Rupture of Membranes	
RSI	Reference Safety Information	
SAE	Serious Adverse Event	
SAR	Serious Adverse Reaction	
SDV	Source Data Verification	
SPC	Summary of Product Characteristics	
SOP	Standard Operating Procedure	
SUSAR	Suspected Unexpected Serious Adverse Reaction	
TMF	Trial Master File	
TSC	Trial Steering Committee	
WHO	World Health Organisation	

#### TRIAL SUMMARY

Trial Title A pragmatic approach to preventing gestational diabetes and pregnanc						
	hypertensive disorders in obese pregnant women in resource poor settings					
Study Acronym	PAPAGENO					
Clinical Phase	Phase III, Feasibility study					
Trial Design	Randomised Control Trial					
Trial Participants	Pregnant Women					
Planned Number of Participants	100					
Planned Number of Sites	2					
Countries Anticipated to be Involved in Trial	Malawi					
Treatment Duration	From consent to delivery (approximately 12-42 weeks gestation) approximately 30 weeks					
Follow up Duration	28 days postnatal					
Total Planned Trial Duration	18 months					
Overall Objective	The overall objective of this study is to determine the feasibility of a pragmatic placebo controlled-randomised trial of metformin to prevent gestational diabetes and pregnancy hypertensive disorders in obese pregnant women.					
Specific Objectives	
 
A. To assess the number of eligible women recruited into the study.
 
B. To ascertain the proportion of pregnant women presenting at or before 2 weeks gestation [when the intervention will be started].
 
C. To assess adherence to therapy (ascertained by review of diary an returned study medication)
 
D. To determine the proportion of women in the placebo group and proportion of those in the active group (if tested prior to starting metformin) who hav gestational diabetes at 24-30 weeks
 
E. To assess the ability to measure key clinical variables
 
F. To verify the proportion of women who are recruited but then lost to follo up for the primary and secondary outcomes.
 
G. To identify an appropriate method by which we can identify women an avoid double randomisation to address co-enrolment (i.e. GPS hom identifiers, thumb or finger print).
 
					
Primary Endpoint	The ratio of women recruited, expressed as a fraction of the total number of women attending for antenatal care over the recruitment period					
Secondary Endpoints	
 
Number of eligible women who are recruited into the study.
 
Proportion of pregnant women presenting at or before 28 weeks gestation [when the intervention will be started].
 
Adherence to therapy (ascertained by review of diary and returned study medication)
 
Proportion of women in the placebo group and proportion of those in the active group (if tested prior to starting metformin) who have gestational diabetes at 24-30 weeks
 
Ability to measure key clinical variables:
 
Proportion of women who are recruited but then lost to follow up for the primary and secondary outcomes.
 
Identify an appropriate method by which we can identify women and avoid double randomisation to address co-enrolment (i.e. GPS home identifiers, thumb or finger print).
 
Adverse events in each group
 
					

IMP(s)	(s) Metformin or placebo					
IMP Route of Administration	Oral					
NIMP(s)	N/A					
	This is a feasibility study of a randomised clinical trial of metformin (compared with matched placebo) for the prevention of gestational diabetes and pregnancy hypertensive disorders in obese pregnant women. This study will help to determine whether we can recruit enough women to conduct a larger trial in the future, to measure if the routine administration of metformin could prevent gestational diabetes and pregnancy hypertensive disorders in obese pregnant women in resource poor settings (in Malawi and Zambia).					
Lay Summary of Trial	Gestational diabetes (too much sugar in the blood in pregnancy) and pregnancy hypertensive disorders (high blood pressure that occurs in pregnancy) both cause maternal and neonatal deaths and long term problems. Gestational diabetes with an estimated global prevalence of 16% (with higher rates in in South Asia and Africa) increases the incidence of the adverse pregnancy outcomes. If left untreated it also increases the risk of future obesity and diabetes. Pregnancy hypertensive disorders account for 17.3% of maternal deaths in low income countries, and are the second commonest cause of maternal death after haemorrhage (severe loss of blood).					
Lay Summary of That	In resource rich countries, testing for gestational diabetes is routinely undertaken in women considered high risk, together with treatment of those affected and regular monitoring. Such an approach is difficult and inappropriate in resource poor settings due to the high cost of testing of blood sugar monitoring and the lack of availability of suitable and cost effective equipment. However, measurements of maternal body mass index (weight and height) cheaply and effectively identifies obese women who are a high-risk group for both gestational diabetes and pregnancy hypertensive disorders.					
	Additionally, one of the current treatments (metformin) for gestational diabetes is relatively cheap, widely available, and is safe, regardless of blood sugar levels. Recent evidence suggests that metformin might also reduce the incidence and severity of pregnancy hypertensive disorders.					
	In this feasibility study we will measure if women are willing to be recruited and take a medication. We will then use this information to determine, if a larger study to prevent gestational diabetes could be conducted in the future.					

#### 1. INTRODUCTION

#### 1.1 BACKGROUND

The estimated global prevalence of gestational diabetes (GDM) is 16%, with higher rates in South Asia and Africa (Federation 2015). GDM increases the incidence of the adverse outcomes of caesarean section, pregnancy hypertensive disorders, birth injury, future obesity and future diabetes: untreated, it contributes to a cycle which promotes obesity and diabetes in future generations (NICE 2015). Pregnancy hypertensive disorders account for 17.3% of maternal deaths in low income countries, and are the second commonest cause of maternal death after haemorrhage (Collaborators 2016). Overweight and obesity rates are increasing rapidly in women of reproductive age throughout the world. Obesity increases the incidence of both gestational diabetes and pregnancy hypertensive disorders (Poston, Caleyachetty et al. 2016): hence obese women will be the focus of our study.

This project aims to ascertain if women are willing to be recruited, and take a medication to prevent (and/or reduce the adverse consequences of) gestational diabetes and pregnancy hypertensive disorders in obese pregnant women in Malawi. For the purpose of this study, we will use an ethnic-specific body mass index (BMI) threshold of  $\geq 26 \text{ kg/m}^2$  in African women to define obesity, given evidence that African ethnicity lowers the BMI risk threshold for diabetes in non-pregnant people (Chiu, Austin et al. 2011). Hence reference to "obesity" from sections 2 onwards of this study means a BMI of  $\geq 26 \text{ kg/m}^2$ .

# **1.2** RATIONALE FOR STUDY

Gestational diabetes and pregnancy hypertensive disorders are an increasing threat to maternal and fetal health in both resource rich and resource poor settings. The prevalence of gestational diabetes is rising, driven by obesity and high glycaemic diet (Berntorp 2016). A systematic review of previously published literature showed the reported prevalence of gestational diabetes in Africa is between 0 % and 13.9% (Macaulay, Dunger et al. 2014). Using the newer World Health Organisation criteria for hyperglycaemia, a subsequent comprehensive global analysis has suggested that the true incidence of diabetes in pregnancy in Africa is higher at around 17%, with 80% of such women having gestational diabetes (Guariguata, Linnenkamp et al. 2014). There are few good estimates of the prevalence of pregnancy hypertensive disorders in Africa: but a WHO estimate of the prevalence of the more severe forms of the condition (pre-eclampsia and eclampsia) in women with BMI  $\geq$  26 is 4.9% (Bilano, Ota et al. 2014).

This trial will address the increasing importance of non-communicable disease in the global burden of ill health, the rising prevalence of obesity and diabetes throughout sub Saharan Africa (including in Malawi) and strategic development goal 3. There is no coherent approach to screening and treatment for gestational diabetes in Malawi and therefore no mitigation of the risks associated with gestational diabetes. In resource rich settings, treatment of gestational diabetes with drugs to lower blood glucose is proven to significantly reduce the risk of short term adverse outcomes and likely reduces the risk of long term adverse outcomes (Farrar, Simmonds et al. 2017). In resource rich settings, this also involves formal glucose tolerance testing, and four times daily monitoring of blood glucose for women found to have gestational diabetes. Such an approach is impractical in resource poor settings because of the high cost of

testing and monitoring per patient (estimated to be £28.58 and £112.07 per pregnancy respectively, 2015 NHS costs) and the irregular availability of glucose monitoring strips. However, metformin endorsed as first line treatment for gestational diabetes in the UK (metformin) is relatively cheap (£11.68 per pregnancy (Excellence 2008)), safe to give without blood glucose monitoring (even for women who are normoglycaemic) (Chiswick, Reynolds et al. 2015, Syngelaki, Nicolaides et al. 2016), and widely available. We propose that, in high risk groups (obese women) routine treatment with metformin, without formal testing for gestational diabetes and without blood glucose monitoring, is a pragmatic approach to preventing and treating gestational diabetes in resource poor settings (which we will test in a trial called PAPAGENO), and will result in improved health care outcomes.

This trial is timely because it makes use of new information on the effect of metformin in obese women without gestational diabetes, where metformin reduces gestational weight gain and pre-eclampsia, is well tolerated and has no major adverse effects (Chiswick, Reynolds et al. 2015, Syngelaki, Nicolaides et al. 2016, Romero, Erez et al. 2017). Notably, *in vitro* studies support a beneficial effect of metformin in reducing pregnancy hypertensive disorders (Brownfoot, Hastie et al. 2016). Together with information on the efficacy of metformin in pregnant women with GDM (Rowan, Hague et al. 2008), these studies pave the way for the strategy we propose here, using metformin without formal testing or monitoring in an unselected group obese women. We anticipate a reduction in GDM and pregnancy hypertensive disorders and we can be confident that women with normoglycaemia will not be harmed.

We hope that this study will show that a larger trial conducted in the future to test metformin as a pragmatic approach to preventing and treating gestational diabetes and pregnancy hypertensive disorders in obese pregnant women in resource poor settings is feasible. Additionally, we anticipate that we will identify the high prevalence of GDM and pregnancy hypertensive disorders in obese pregnant women. It is hoped that the results of this feasibility study will facilitate a funding application for a definitive randomised trial of metformin in this scenario following which we hope to show that universal treatment of overweight/obese pregnant women with metformin is effective in reducing GDM and pregnancy hypertensive disorders, safe, easy to implement and affordable. If so, since metformin is cheap and widely available (on the WHO essential medicines list), such a strategy could be rolled out in other Low and Middle Income Countries (LMIC). Inclusion of policy makers in our collaborative group will facilitate wide implementation.

#### 2. STUDY OBJECTIVES

#### 2.1 SMART OBJECTIVES

#### 2.1.1 Overall Objective

The overall objective of this study is to determine the feasibility of a pragmatic placebo controlled randomised trial of metformin to prevent gestational diabetes and pregnancy hypertensive disorders in obese pregnant women.

#### 2.1.2 Specific Objectives

- A. To assess the number of eligible women recruited into the study.
- B. To ascertain the proportion of pregnant women presenting at or before 28 weeks gestation [when the intervention will be started].
- C. To assess adherence to therapy (ascertained by review of diary and returned study medication)

- D. To determine the proportion of women in the placebo group and proportion of those in the active group (if tested prior to starting metformin) who have gestational diabetes at 24-30 weeks
- E. To assess the ability to measure key clinical variables like incidence of gestational diabetes and pregnancy hypertensive disorders in women with BMI
   ≥ 26 kg/m2 in this setting, the proportion of women who present early in pregnancy (<20 weeks gestation) and are eligible for recruitment

- F. To verify the proportion of women who are recruited but then lost to follow up for the primary and secondary outcomes.
- G. To identify an appropriate method by which we can identify women and avoid double randomisation to address co-enrolment (i.e. GPS home identifiers, thumb or finger print).

# 2.2 ENDPOINTS

# 2.2.1 Primary Endpoint

For this trial, the primary endpoint is the ratio of women recruited, expressed as a fraction of the total number of women attending for antenatal care over the recruitment period

# 2.2.2 Secondary Endpoints

- A. Number of eligible women who are recruited into the study.
- B. Proportion of pregnant women presenting at or before 28+0 weeks gestation [when the intervention will be started].
- C. Adherence to therapy (ascertained by review of diary and returned study medication)
- D. Proportion of women in each of the placebo group and the active group (if tested prior to starting metformin) who have gestational diabetes between 24+0-30+6 weeks
- E. Ability to measure key clinical variables:
  - The incidence of gestational diabetes and pregnancy hypertensive disorders in women with BMI  $\ge$  26 kg/m^2in this setting
  - Feasibility of recruitment and randomisation
  - The proportion of women who present early in pregnancy (<20 weeks gestation) and are eligible for recruitment
  - The proportion of eligible women (and clinicians) are willing to participate in the study and be randomised (or randomise) to metformin or placebo?
  - In what proportion of women can we record other secondary outcomes planned for the substantive trial
  - The proportion of women who have an ultrasound scan before 20 weeks gestation so that gestational age can be determined.
  - The resources are required for outcome data ascertainment and collection
- F. Proportion of women lost to follow up for the primary and secondary outcomes.
- G. Determination of an appropriate method by which we can identify eligible women and avoid double randomisation to address co-enrolment (i.e. GPS home identifiers, thumb or finger print).

# 3. STUDY DESIGN SUMMARY (PICO)

This is a feasibility study of a double masked randomised clinical trial of metformin (compared with matched placebo) for the prevention of gestational diabetes and pregnancy hypertensive disorders in women at high risk of both conditions.

**Population**: 100 pregnant women (BMI  $\ge$  26 kg/m^2) in Malawi.

**Intervention**: Metformin oral tablets (500mg slow release), up to 2000mg daily from consent (first visit) until delivery.

**Comparator:** Matched placebo taken with same frequency over the same duration of pregnancy again taken in addition to the current standard of care

Duration of trial: First participant's first visit to the last baby delivered plus 28 days.

**Treatment Phase:** The treatment phase will be from first visit (expected to between  $12^{+0}$  to  $28^{+0}$  weeks gestation) until delivery. Follow up will continue for 28 days after delivery.

#### Outcomes:

Primary: The ratio of women recruited, expressed as a fraction of the total number of women attending for antenatal care over the recruitment period

Secondary outcomes: Proportion of pregnant women presenting at or before 20 weeks gestation, adherence to therapy (ascertained by review of diary and returned study medication) and clinical staff ability to measure key clinical variables.

**Stopping Rules:** Stopping rules are detailed in section 11.3.

#### 4. STUDY POPULATION

#### 4.1 NUMBER OF PARTICIPANTS

We aim to recruit 100 eligible women in total.

#### 4.2 INCLUSION CRITERIA

To be eligible to take part in the PAPAGENO study, the below inclusion criteria must be met:

- (i) Pregnant women with a BMI  $\ge$  26 kg/m^2
- (ii) Pregnant Women between  $\ge 12^{+0}$  and  $\le 28^{+0}$  weeks gestation
- (iii) Women estimated age  $\geq$  18 years
- (iv) Women with a signed (and witnessed, if applicable) informed consent
- (v) Willing to be contacted, if necessary.

#### 4.3 EXCLUSION CRITERIA

- A. Conditions identified in the current pregnancy, which exclude study participation:
  - Women with a BMI < 26 kg/m^2
  - Pregnancy gestation > than 28+0 weeks
  - Women who are known to have a multiple pregnancy at the time of trial entry

PAPAGENO: Protocol Version 1.0 07/03/2019 Page 16 of 46

- Women who are currently lactating
- Women known to have diabetes
- Women who have been taking HIV antiretroviral medication for less than 6 months
- Women currently taking dolutegravir
- Acute conditions at the time of trial entry with the potential to alter renal function such as:
  - Dehydration sufficient to require intravenous infusion
  - severe infection
  - o shock

0

- o intravascular administration of iodinated contrast agents
  - acute or chronic diseases which may cause tissue hypoxia such as:
    - cardiac or respiratory failure,
    - Pancreatitis
    - recent myocardial infarction,
    - hepatic insufficiency, acute alcohol intoxication, alcoholism
- B. History of the following pre-existing conditions, at the time of trial entry:
  - Had a previous delivery of a baby <3rd centile for gestational age (e.g. a baby born ≥ 37 weeks gestation and the birthweight was ≤2.25KG)
  - A known history in a previous pregnancy of gestational diabetes (needing drug treatment)
  - A known history of conditions affecting either the heart, lungs, liver, kidney or brain, which require regular medication at the time of recruitment
  - A known history of allergy to metformin or to any of the ingredients as listed in the current Summary Products Characteristics (SPC))
  - Known liver failure or dysfunction at the time of trial entry
  - Known severe renal failure or dysfunction at the time of trial entry
  - Known (any type of) acute metabolic acidosis (such as lactic acidosis, diabetic ketoacidosis)
  - A previous known diabetic pre-coma
  - Previous known severe renal failure (GFR < 30 mL/min).

Note, the exclusion conditions listed in B above do not require additional testing to identify them. It is not currently clinical practice to perform formal testing for these conditions prior to giving metformin. Additionally testing to exclude all conditions will add an additional burden to Low Middle Income Country involved. However, the investigator(s) will review the woman's medical history by asking the woman questions and using available information to determine, if the woman has had any of these conditions.

Note, although metformin is not licensed for use during pregnancy its use in this scenario is endorsed by the National Institute for Health and Care Excellence.

# 5. CO-ENROLMENT

Women involved in other non-CTIMP trials will be permitted to co-enrol. Women in other CTIMPs will be eligible for co-enrolment at the discretion of the Chief Investigator for both studies. The local PI should contact the CI to seek advice and confirmation for co-enrolment. A record of all co-enrolled trials will be maintained and the woman's participation recorded in the eCRF.

# 6. PARTICIPANT SELECTION AND ENROLMENT

# 6.1 IDENTIFYING PARTICIPANTS

Current clinical practice is that on arrival at the antenatal clinic all women are weighed and their height measured. Height is recorded as <than 150cm or >than 150cm on the health passport carried by each woman. Women then attend a health education class (which lasts 15- 30 minutes). For the purpose of the study, all women in attendance will be provided with verbal information about the study and asked to present themselves to a member of staff, if they are interested in participating. Each woman is also reviewed by the local clinician (usually an obstetrician or midwife) and if considered potentially eligible she will be given further verbal and written information.

### 6.2 SCREENING FOR ELIGIBILITY

Women with a pregnancy between  $\geq 12^{+0}$  and  $\leq 28^{+0}$  week gestation and with a height recorded as less than 150cm and a weight  $\geq$  than 55kg (BMI equivalent 26) or a height > than 150cm and a weight greater than 60kg (BMI equivalent 26) will be reviewed by an appropriately trained, individual/delegated clinicians who will calculate their actual BMI, with repeat measurements of height and weight as required. Since measurement of height and weight is carried out routinely, we will not seek formal written consent for this. Further eligibility criteria will be ascertained from the patient notes / history. Again, given these questions are routine, we will not seek formal consent to determine initial eligibility. Women who appear to fulfil the inclusion criteria will be asked if they wish to participate in the study. An anonymised screening log will be maintained on the eCRF for all patients considered eligible for the trial, including those who decline to participate. The log will include estimated maternal age, gestation and BMI at presentation, as well as any exclusion reason or reasons (if provided) for declining. Eligibility will be confirmed by an obstetrician before randomisation.

If a participant declines to participate, withdraws prior to randomisation, or is excluded following consent but prior to randomisation for any reason, the minimal anonymised information will remain on the screening log. If participants are willing to offer a reason for declining to participate, this will also be held on the screening log.

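### The pre-screening weights in section 6.2 do not correspond to BMI 26 across their height bands, so the rule passes over some eligible short women and leaves out a height of exactly 150 cm

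*Protocol*

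**What the plan says.** Entry depends on BMI. Protocol section 4.2 admits "Pregnant women with a BMI" of 26 kg/m² or more, and section 4.3 excludes "Women with a BMI < 26 kg/m 2".

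Section 6.2 puts a coarse sift in front of that criterion. Among women at 12 to 28 weeks, two groups are passed to a trained clinician: those with a "height recorded as less than 150cm" and a weight at or above 55 kg, and those above 150 cm who weigh more than 60 kg. The wording of the two cut-offs, with the label on each, is "than 55kg (BMI equivalent 26) or a height > than 150cm and a weight greater than 60kg (BMI equivalent 26").

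The clinician is the person "who will calculate their actual BMI, with repeat measurements of height and weight as required".

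Section 6.1 describes the routine record that the sift relies on: "Height is recorded as <than 150cm or >than 150cm on the health passport carried by each woman". It also says that every attender hears about the study and may come forward if interested, and that a local clinician reviews each woman for potential eligibility.

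**The concern.** A fixed weight corresponds to a given BMI at one height only. Section 6.2 attaches the same BMI label to one weight for every height below 150 cm and to another for every height above it. Where a cut-off exceeds the weight that gives BMI 26 at a woman's height, she meets the inclusion criterion but fails the sift. Both height conditions are strict inequalities, so exactly 150 cm satisfies neither, and the passport categories in section 6.1 have the same gap.

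This matters because recruitment and eligibility are what this feasibility study measures. Secondary endpoints A and E (section 2.2.2) rest on counts of eligible women. The primary endpoint (section 2.2.1) divides women recruited by all antenatal attenders, so a missed woman stays in the denominator and cannot reach the numerator through this route. On the screening log (sections 6.2 and 6.3) she is either absent or entered as ineligible when she is not. The misses depend on height, and a larger trial that copied the rule would repeat them.

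**Working it through.** **Inputs, all from the protocol.** Threshold BMI 26 (4.2, 4.3). Below 150 cm: weight ≥ 55 kg. Above 150 cm: weight > 60 kg (6.2).

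**Formulae.** BMI = w / h², with w in kg and h in metres. Weight at BMI 26 = 26 × h². Height at which weight w gives BMI 26 = √(w / 26).

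**Can the labels be reproduced?** At 150 cm, the only height the rule names:

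- 55 / 1.50² = 24.4
- 60 / 1.50² = 26.7
- 26 × 1.50² = 58.5 kg

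Neither label holds there. Solving for the height at which each does:

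- √(55 / 26) = 1.454 m
- √(60 / 26) = 1.519 m

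Each label is true at one height within its band and nowhere else.

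**Who is missed?**

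| Height (cm) | Weight at BMI 26 (kg) | Cut-off that applies | BMI at cut-off | Eligible on BMI but fails the sift |
|---|---|---|---|---|
| 140 | 50.96 | ≥ 55 | 28.06 | 51.0 to 54.9 kg |
| 144 | 53.91 | ≥ 55 | 26.52 | 54.0 to 54.9 kg |
| 149 | 57.72 | ≥ 55 | 24.77 | none |
| 150 | 58.50 | none | n/a | 58.5 kg and above |
| 151 | 59.28 | > 60 | 26.31 | 59.3 to 60.0 kg |
| 155 | 62.47 | > 60 | 24.97 | none |
| 160 | 66.56 | > 60 | 23.44 | none |

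There are three gaps: heights below 145.4 cm, heights just over 150 to 151.9 cm, and exactly 150 cm. At other heights the cut-offs are too low, which only sends forward women whom the actual BMI then removes.

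**How many?** The protocol gives no height or BMI distribution, so these are assumptions. Take mean height 154 to 158 cm (SD 6) and mean BMI 23.5 to 26.5 (SD 3.5 to 4.5), with lognormal BMI independent of height. Simulation gives:

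- 0.6 to 3.3% of all BMI-eligible women missed by the weight cut-offs;
- 14 to 29% of eligible women below 145.4 cm missed; they are only about 1.8 to 7.6% of eligible women, so this part is 0.3 to 2.2% of the total;
- about 5 to 10% of eligible women at 150 to 152 cm missed;
- 2.7 to 5.4% of eligible women recorded at exactly 150 cm if height is rounded to the nearest centimetre. This group overlaps slightly with those already counted just above 150 cm.

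A second set of assumptions (mean height 153 to 160 cm, SD 6; median BMI 23 to 25, log-SD 0.16) gives 0.4 to 4.1% missed by the weight cut-offs and 1.7 to 5.8% at a rounded 150 cm.

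**Effect on the primary ratio.** If missed women would have joined at the same rate as the others, losing 0.6 to 3.3% of them multiplies the ratio by 0.994 to 0.967. The relative sampling error of a count of 50, the number behind the ratio used for planning in section 11.2, is about 1 / √50 = 14%.

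**The case against.** The strongest reply is that this is a first sift built on a two-category height record, not an eligibility rule. It errs towards inclusion at most heights, actual BMI is calculated before entry, and an obstetrician confirms eligibility before randomisation. That stands: a reader might infer that the wrong labels let ineligible women in, and the protocol does not support this.

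A reader might also infer that the missed women are never assessed. That is too strong. Section 6.1 allows self-presentation and local clinician review, and section 6.2 does not forbid calculating BMI for other women. But section 6.1 states no BMI rule, a height category alone cannot yield a BMI, and section 6.2 provides the calculation only for women who pass the cut-offs. Those routes reduce the loss without correcting the rule.

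On 150 cm, clinic staff with two boxes would presumably choose one. That is plausible, but the protocol does not say which.

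A third tempting reading is that the primary result is materially distorted. It is not: section 11.1 expects over 100 new women a week at the main site against a need of 8 to 9 recruits a month, and the bias is well below sampling error.

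**Conclusion.** The point holds as an arithmetic and boundary error in an operational threshold. The labels are wrong at the height where the bands meet, two ranges of short women who satisfy section 4.2 are not routed to the BMI calculation, and 150 cm is unassigned. These facts need no assumption beyond the protocol's own figures.

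The size does rest on assumptions. With the height and BMI distributions stated above, about 0.6 to 3.3% of BMI-eligible women fail the weight cut-offs, plus any recorded at exactly 150 cm. These are upper figures to the extent that some women come forward by the section 6.1 routes. The effect falls mainly on the counts of eligible women and the screening log, and only slightly on the primary ratio. It would not change the feasibility conclusion. It is worth correcting because those counts are outputs of the study and the correction is simple.

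**What to change.** Keep the two-band sift in section 6.2 and change four things:

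- For heights of 150 cm and above, use a weight of at least 58.5 kg (26 × 1.50²).
- Below 150 cm, use 26 × h² at a stated minimum height, and name that height. For 140 cm this is 26 × 1.40² = 50.96, about 51 kg; for 135 cm it is 47.4 kg. Round down rather than up, and calculate BMI directly for any shorter woman.
- Assign 150 cm to a band, as above, and tell clinic staff which passport category to use for it.
- Delete the BMI 26 labels.

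The cost is a change of wording and some extra BMI calculations for women who prove ineligible.

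The alternative is to calculate BMI directly for every woman whose exact measured height is recorded, which closes all three gaps. It is more than a wording change: section 6.1 says height is measured but recorded only as below or above 150 cm, so exact height would have to be captured at a clinic seeing over 100 new women a week.
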